10. STUDY DRUG MATERIALS AND MANAGEMENT

10.1 Description of Study Drug

A novel topical vitamin D3 (cholecalciferol) gel has been developed and is being provided by Innovative Pharmacy Solutions, Inc. The ingredients in the gel are well-known in the industry and have references in the pharmaceutical literature and some have available FDA drug master file information. The formulation for the topical vitamin D gel is:

Gel Formula

Vitamin D3 1,000,000 IU/gm	20.0 gm
Phosol 53 MCT (lipoid)	20 gm
Cholesterol USP-NF	0.8 gm
Isopropyl myristate USP-NF	5 gm
Poloxamer 407 NF	7.5 gm
Purified Water USP	46.5 gm
Methylparaben USP-NF	0.18 gm
Propylparaben USP-NF	0.02 gm

The previous anhydrous formula was changed to a hydrous base to provide a less greasy product. The new formula is a simple wash off base that provides phospholipids that are able to self-associate into micelles and liposomes.

[figure not shown]
10.2 Packaging and Labeling

The topical vitamin D gel is provided in a syringe as a single application of 0.75g of gel, containing 150,000 IU of vitamin D3 (cholecalciferol) that will be applied to each of the subject's upper arms, totaling 300,000 IU per dose.

Labeling of study drug will comply with regulatory requirements as follows:

II.G. Labeling

II.G. 1. Anhydrous Base

II.G. 2. Drug Product

1. The label for the syringe with the final product will include the product name, strength and quantity, mixing date, beyond use date, name of the pharmacy compounding the product (Innovative Pharmacy Solutions), IND number, RPh name that compounded and dispensed and auxiliary labels “Keep Refrigerated” and “CAUTION New Drug – Limited by Federal law to Investigational Use.”

**Innovative Pharmacy Solutions
IND# 110937**
Vitamin D3 in Hydrous Base 200,000 IU/mL
Quantity: 0.25ml 50,000 IU VitaminD3
Mix Date: 7.28.2015 Beyond Use Date: 7.28.2015
RPh name: Toll Free [contact]
KEEP REFRIGERATED
CAUTION New Drug - Limited by Federal Law to Investigational Use

2. The ziplock bag label will contain the compounding pharmacy name (Innovative Pharmacy Solutions), address, phone number and after hours phone number, IND number, “Keep Refrigerated” and “CAUTION New Drug – Limited by Federal law to Investigational Use.”

**Innovative Pharmacy Solutions
IND# 110937**
[name]
Minnesota Pharmacy License # 263570
Pharmacy [contact]
[name] Cell [contact] Toll Free [contact]
KEEP REFRIGERATED
CAUTION New Drug - Limited by Federal Law to Investigational Use

3. The 1 mL syringe labels will contain the product name and “For Left Arm administration” or “For Right Arm administration”, IND number, and “CAUTION New Drug – Limited by Federal law to Investigational Use.”

For Left Arm Administration
50,000 IU Vitamin D3 in Anhydrous Base 0.25 ml
IND# 110937
CAUTION New Drug - Limited by Federal Law to Investigational Use

For Right Arm Administration

50,000 IU Vitamin D3 in Anhydrous Base 0.25 ml

IND# 110937

CAUTION New Drug - Limited by Federal Law to Investigational Use

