We will initially administer 100,000 units topically to subjects, and check serum Vitamin D and calcium levels one week later. Dosing will be discontinued if a patient achieves a Vitamin D level of greater than normal (> 90 ng/ml) or if serum calcium rises above normal (> 10.2 mg/dl). Additional doses of 100,000 units will be administered on days 7 and 14. The outcome of interest will be the effect on total serum Vitamin D at 21 days. Although a change in calcium is unlikely, calcium will be monitored for safety.

Vitamin D may alter glucose values and improve glucose control in individuals with diabetes²⁶. Although individuals with diabetes will not be excluded, we will instruct any subjects with diabetes to more closely monitor glucose values during the course of the study.

Parathyroid hormone will be measured at baseline and on Day 21 to determine if vitamin D correction changes the level of this metabolic calcium regulatory hormone.

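### The syringe labels and the Section 13.1.1 dosing text give one third of the design dose, and the primary outcome text in both documents repeats the lower figure

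*Protocol*

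**What the plan says.** Most of the protocol gives one dose. Section 7.1 specifies 150,000 IU in 0.75 mL per arm and 300,000 IU weekly for three weeks. The Synopsis product description, the product development text in 5.1, and Section 6 agree on dose. Sections 9.2 and 10.3 give 0.75 mL per arm. Section 5.2.2 gives the 900,000 IU total. Section 10.2 itself opens by describing the syringe as "a single application of 0.75g of gel, containing 150,000 IU of vitamin D3 (cholecalciferol").

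Other current text gives a different dose:

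- **Main syringe label, Protocol 10.2.** Strength "Vitamin D3 in Hydrous Base 200,000 IU/mL"; fill "Quantity: 0.25ml 50,000 IU VitaminD3". The fill is a required label field: "The label for the syringe with the final product will include the product name, strength and quantity".
- **Left- and right-arm labels, Protocol 10.2.** Each reads "50,000 IU Vitamin D3 in Anhydrous Base 0.25 ml".
- **Protocol 13.1.1.** "We will initially administer 100,000 units topically to subjects", and then "Additional doses of 100,000 units will be administered on days 7 and 14". The same paragraph holds the individual stopping limits.
- **Primary outcome, Protocol 14.3.5 and SAP 1.3.5.** Both describe the change after 100,000 IU weekly for three weeks.
- **Synopsis, application step.** It gives 0.25 mL per syringe, although the Synopsis elsewhere gives 0.75 g and 150,000 IU per applicator.

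Nothing in the text reconciles the two levels, for example through dose escalation or several syringes per arm.

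**The concern.** The study has one treatment at one dose, and the documents give two values for it that differ by a factor of three. The lower value is not an isolated slip. The label quantity, the safety dosing text, the synopsis volume and the primary outcome fit together as a complete alternative regimen, so a reader meeting any one of them would not see an obvious error.

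Every description of the application has the entire syringe emptied onto the arm, so the amount the pharmacy puts in the syringe is the dose. The syringe does not limit the fill to one volume: "The 1 mL syringe labels will contain the product name", and a 1 mL syringe holds either 0.25 or 0.75 mL. If the labels are printed as shown, one of two faults follows:

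1. **The fill matches the label.** Subjects receive one third of the design dose. The rule that stops the study when the change is consistently below 10 µg/L in the first 10 subjects (Synopsis; 5.2.2) would then be judged on a dose the design did not intend. Section 5.2.2 already reports an insignificant average change in three candidates given 300,000 units in total over three weeks.
2. **The fill matches the design.** Every label understates its contents threefold, and 13.1.1 describes one third of the actual exposure.

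Separately, the primary outcome text attributes the result to a regimen the design does not give. In the SAP, 100,000 IU weekly is the only dose stated anywhere.

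**Working it through.** **Inputs.** Gel formula (10.1): 20.0 g of vitamin D3 at 1,000,000 IU/g plus the other listed ingredients. Design volume: 0.75 g or 0.75 mL per syringe (7.1, 9.2, 10.2 opening, 10.3). Label volume: 0.25 mL (10.2). Label strength: 200,000 IU/mL (10.2). Two arms per dose and three doses. Grams and millilitres are treated as equal, as the documents do.

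**Step 1: reproduce the plan's strength and syringe content.**

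Batch mass = 20 + 20 + 0.8 + 5 + 7.5 + 46.5 + 0.18 + 0.02 = 100.00 g.

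Strength = 20 g × 1,000,000 IU/g ÷ 100 g = 200,000 IU/g. This matches the label strength and Section 7.1 (150,000 IU ÷ 0.75 mL = 200,000 IU/mL).

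The strength is therefore consistent throughout, and the stated 150,000 IU per syringe is reproduced: 0.75 × 200,000 = 150,000. The conflict is in volume and dose only.

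**Step 2: compare the two regimens.** Dose = strength × volume × 2 arms; total = dose × 3.

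| | Design | Label | Shortfall |
|---|---|---|---|
| Volume per syringe | 0.75 mL | 0.25 mL | 0.50 mL |
| Per syringe | 150,000 IU | 50,000 IU | 100,000 IU |
| Per dose (× 2) | 300,000 IU | 100,000 IU | 200,000 IU |
| Over three doses (× 3) | 900,000 IU | 300,000 IU | 600,000 IU |

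Ratio = 300,000 ÷ 100,000 = 3. Relative shortfall = 600,000 ÷ 900,000 = 66.7%.

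**Step 3: match the lower figures to each other.** The label gives 100,000 IU per dose, which is the figure in 13.1.1, 14.3.5 and SAP 1.3.5. The synopsis volume of 0.25 mL gives the same result at the label strength.

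**Step 4: extent if the label were followed.** 2 arms × 3 doses = 6 syringes per subject; × 10 subjects = 60 syringes by the time of the stopping check.

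**The case against.** The strongest reply is that the intended dose is not in doubt and the lower figures are leftovers. Section 5.2.2 reports that 300,000 units over three weeks had little effect in the first three candidates and then sets three doses of 300,000 IU. The figure of 100,000 IU weekly for three weeks adds up to that earlier total. The label block looks imported: its numbering (II.G.) does not belong to the protocol, and its mix and beyond-use dates are the same day in July 2015, whereas one of the protocol's references was accessed in November 2015. Its item 1 lists label fields and is not a fill instruction. The only fill statement in 10.2 is the correct opening sentence, and preparation instructions sit in Appendix 1. Supervised application at a stated 0.75 mL might reveal a short fill, and exposure reporting covers cumulative dose. Early termination would need the mis-fill to pass unnoticed in essentially all of the first 10 subjects.

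Much of this stands. It identifies which dose is intended and lowers the probability of a mis-fill, so early stopping is only a possibility. It does not remove the error:

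- The main label names the hydrous base, which 10.1 describes as the new formula, yet still carries the lower quantity. The base was updated there and the fill was not.
- Section 10.2 presents these labels as how the product will be labelled. They are the only label text available, and Appendix 1 was not available to check.
- A check against the synopsis application step would confirm 0.25 mL.
- Protocol 14.3.3 and SAP 1.3.3 measure compliance against a target dose that they do not state.

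**Conclusion.** The concern holds. Current text in both documents contradicts the design dose by a factor of three: 50,000 against 150,000 IU per syringe, 100,000 against 300,000 IU per dose, and 300,000 against 900,000 IU per subject. Confidence in the contradiction is high, and it should be corrected before syringes are prepared.

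The consequence is less certain. Underdosing by 67% requires the pharmacy to fill to the label, and a wrong stopping decision requires that to persist across the first 10 subjects. No response is projected from the three earlier candidates, because the gel base they received is not stated.

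The calculated change in 25-OH vitamin D, the sample size calculation and the absolute stopping limits in 13.1.1 (above 90 ng/ml for vitamin D, above 10.2 mg/dl for calcium) do not depend on which dose is written and are unaffected. Treating grams and millilitres as equal does not affect the threefold ratio.

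**What to change.** State 150,000 IU in 0.75 mL per arm, 300,000 IU per dose, in each of these places:

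- the application step in the Protocol Synopsis (0.75 mL in place of 0.25 mL);
- the main label and both arm labels in Protocol 10.2 (0.75 mL, 150,000 IU);
- the dosing sentences in Protocol 13.1.1 (300,000 units at the first dose and on days 7 and 14);
- the primary outcome in Protocol 14.3.5 and SAP 1.3.5 (300,000 IU weekly for three weeks).

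Replace the anhydrous base wording on the arm labels, and in the label block's subheading, with the hydrous base. Confirm that the preparation instructions in Appendix 1 give the same fill. As a clarification, name 300,000 IU per dose as the target dose in Protocol 14.3.3 and SAP 1.3.3.

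The cost is wording in the two documents and corrected label text. No patients, visits or procedures are added.

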10.3 Study Drug Administration

A study nurse or physician will supervise each treatment application to ensure that the gel is applied correctly. Prior to application of the gel, 2 strips of paper tape will be applied to the subject's upper arms. One strip will be applied approximately 2 inches below the subject's shoulder and the second strip will be applied approximately 2 inches above the subject's elbow. The entire contents of one syringe (0.75 mL of gel) will be applied onto each arm in a straight line, from approximately 1 inch below the first strip of paper tape to approximately 1 inch above the second strip of paper tape. The subject will be instructed to gently rub the gel into their upper arm with their fingertips, while staying between the two pieces of paper tape, for approximately 2 minutes or until the gel has been absorbed. After completing the application process on both arms, the subject will wash his/her hands thoroughly.

Handling and Storage of Study Drug

Specific instructions for preparing and administering the topical vitamin D gel are provided in Appendix 1.

11. STUDY ASSESSMENTS AND PROCEDURES

The schedule of study assessments and procedures is shown in Table 1.

11.1 Baseline Assessments

A chart review of subjects with known vitamin D deficiency will be performed prior to Day 0 in order to assess for potential study eligibility. Informed consent must be obtained before any study procedures are performed.

11.1.1 Study Day 0

The following procedures should be completed on Day 0:

- informed consent
- assessment of height, weight and skin to assess for study eligibility
 - Anthropometric Assessment
 - Patients are measured for height (cm) and weight (kg) following standardized procedures as outlined in the Anthropometric Standardization Reference Manual (Lohman et al., 1991). Body weight is measured with a stand-on digital scale and height is measured by a stadiometer. Height is measured to the nearest 0.1 cm and weight to the nearest 0.1 kg.
 - Recording of Fitzpatrick skin-type score.
- Blood draw for vitamin D level, parathyroid hormone level, calcium, and albumin.
- Application of the topical vitamin D gel, including instructions for dosing at home

11.1.2 Study Day 7 and Study Day 14

- Evaluation of skin site where gel applied. If the subject has any skin rash or other reaction, he/she should contact study personnel as soon as possible for photographs and an assessment/diagnosis
 - Photographs of application sites
 - A digital photograph may be taken of the gel application site following application to record any signs of irritation or reaction. Identifying marks on or near the application site (i.e. tattoos, birthmarks, scars etc.) should be avoided when a photograph is taken. Digital photographs will be uploaded to the REDcap database and stored on the secure server.
- Blood draw for vitamin D level and calcium
- Application of the topical vitamin D gel

11.1.3 Study Day 21

- Assessment of skin for rash or any other reaction
- Blood draw for vitamin D, parathyroid hormone level, and calcium.

12. EFFICACY ASSESSMENTS

Efficacy assessments should be performed according to the Schedule of Events (Table 1).

12.1 Vitamin D Levels

Assessments of serum 25-OH vitamin D levels (D2 and D3) will be done and on Day 0, 7, 14, and 21. Venous blood draws will be performed by a trained University of Minnesota Physicians (UMP) technician and delivered to HealthEast laboratory for analysis.

13. ASSESSMENT OF SAFETY

13.1 Safety Assessments

13.1.1 Skin Rash or Other Reaction

An assessment of each subject's skin will be performed on Days 7, 14 and 21 using the following scoring system for topical irritation developed per FDA guidance:

Basic Score: Description:

- 0 No visible reaction
- 0.5 Doubtful or negligible erythema reaction
- 1.0 Mild or just perceptible macular erythema reaction in a speckled/follicular, patchy or confluent pattern (slight pinking)
- 2.0 Moderate erythema reaction in a confluent pattern (definite redness)
- 3.0 Strong or brisk erythema reaction that may spread beyond the test site

Supplemental Scores: Description: Label:

- 0.5 Edema E
- 0.5 Papules P
- 0.5 Vesicles V
- 0.5 Bullae B

Supplemental scores will be added to the basic scores if the associated symptoms are present. The final score will be the sum of the basic and supplemental scores.

As part of the general safety assessment, dermal irritation will be evaluated by the Investigator or designated research staff using the outlined scale. The likelihood of allergic reaction not manifested as a dermal irritation is extremely low. Given that all the ingredients used to make the topical vitamin D gel are considered GRAS, we do not anticipate non-local allergic reactions. In the event that a non-dermal allergic reaction occurs, standard medical procedures utilized for such situations will be followed.

If a subject develops a dermal response of 1.5 up to 2.5, he or she will be given the option to permanently discontinue the study treatment and withdraw from the study, or to allow sufficient time for the rash to resolve before he or she reinitiates the phase of the study he or she was in at the time that the rash developed. If a participant develops a dermal response of 2.5 or greater, he or she will be required to permanently discontinue the study treatment and he or she will be withdrawn from the study. In both cases, the study participant will be encouraged to seek medical care from his or her primary care physician. In addition, we will ask subjects who decide to withdraw from the study to return for their next scheduled blood draw, as per protocol. We will also follow up with any study participant who withdraws from the study due to AE occurrence through telephone contact at 1 week intervals until the AE resolves.

All other adverse events will be assessed by self-report from subjects.

We will initially administer 100,000 units topically to subjects, and check serum Vitamin D and calcium levels one week later. Dosing will be discontinued if a patient achieves a Vitamin D level of greater than normal (> 90 ng/ml) or if serum calcium rises above normal (> 10.2 mg/dl). Additional doses of 100,000 units will be administered on days 7 and 14. The outcome of interest will be the effect on total serum Vitamin D at 21 days. Although a change in calcium is unlikely, calcium will be monitored for safety.

Vitamin D may alter glucose values and improve glucose control in individuals with diabetes²⁶. Although individuals with diabetes will not be excluded, we will instruct any subjects with diabetes to more closely monitor glucose values during the course of the study.

Parathyroid hormone will be measured at baseline and on Day 21 to determine if vitamin D correction changes the level of this metabolic calcium regulatory hormone.

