1. SYNOPSIS

Study Title:	Vitamin D Levels in Subjects with Vitamin D Deficiency Following Topical Application of Vitamin D Gel – A Proof of Concept Study
Protocol Number:	VITD-001
Development Phase:	Phase 1
Indication:	Subjects with known vitamin D deficiency (<20 µg/L Total 25-OH Vitamin D)
Study Drugs: (Including test, comparator, dosage form, dosing regimen and route)	
A novel vitamin D₃ (cholecalciferol) is provided as a topical gel using ingredients that are identified in the USP/NF and/or designated in the list of Inactive Ingredients in FDA Approved Drugs. The ingredients in the topical gel are well known in the industry and have references in the pharmaceutical literature and some have available FDA drug master file information. A single applicator contains 0.75g of gel, containing 150,000 international units of vitamin D3 (cholecalciferol) to be applied to the upper arm. One dose consists of two applicators, one applied to each upper arm, for a total of 300,000 international units per dose.
 
Subjects with known vitamin D deficiency of ≤20 ng/ml total 25-OH Vitamin D (50 nmol/liter) will be consented and enrolled. They will have a blood draw prior to dosing on Day 1 (to obtain a baseline vitamin D, calcium, albumin, and parathyroid hormone level) and will receive 300,000 units of topical vitamin D3. On Day 7, subjects will return to the clinic for a blood draw to assess Vitamin D level and to check for any signs of skin rash and/or reaction. If a subject has a skin rash and/or reaction prior to Day 7, he/she will be advised to return to the clinic for assessment as soon as possible. Any rash and/or skin reaction may be photographed and diagnosed. A second dose of 300,000 units of topical Vitamin D will be applied by the nurse at the day 7 visit. Subjects will return on Day 14 for a third dose and a third blood draw. A final blood draw to assess for Vitamin D level will be done on day 21.
 
A study nurse or physician will apply each dose of topical Vitamin D. Prior to application of the gel, 2 strips of paper tape will be applied to the subject's upper arms. One strip will be applied approximately 2 inches below the subject's shoulder and the second strip will be applied approximately 2 inches above the subject's elbow. The entire contents of one syringe (0.25 mL of gel) will be applied onto the subjects arm in a straight line, from approximately 1 inch below the first strip of paper tape to approximately 1 inch above the second strip of paper tape. The subject will be instructed to gently rub the gel into their upper arm with their fingertips, while staying between the two pieces of paper tape, for approximately 2 minutes or until the gel has been absorbed. After completing the application process on both arms, the subject will wash his/her hands thoroughly.

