
No. Subjects:	20 subjects will participate. If the change from baseline in 25-OH vitamin D is consistently less than 10 µg/L in the first 10 subjects then the study will be discontinued.
No. Centers:	The study will be conducted at the University of Minnesota (single center)
Study Duration:	The maximum duration of treatment is 14 days (study Days 0, 7 and 14). Subjects will be followed for change in vitamin D blood level and for safety until Study Day 21. It is anticipated that the study will last 4 months to enroll and complete dosing and assessment of 20 patients.
Objectives of the Study:	The primary objective of the study is to determine the change in vitamin D blood levels following 3 doses of topical vitamin D ₃ treatment. The secondary objective is to assess the safety (based on skin rash and/or other reaction, as well as calcium and parathyroid hormone levels) following the application of 3 doses of vitamin D ₃ gel.
Study Endpoints: (Primary and Secondary)	The primary endpoint is to establish the average change in vitamin D blood levels following 3 doses of treatment with vitamin D gel. The secondary study endpoint is the number of subjects who have any skin rash and/or other skin reaction following treatment with the vitamin D gel.
Study Design:	The study is a pre vs. post open-label trial to assess the change in vitamin D blood levels following treatment with 3 doses of topical vitamin D gel. Subjects with known vitamin D deficiency will be consented and enrolled. They will have a blood draw prior to dosing on Day 0 (to obtain a baseline vitamin D level) and will receive topical vitamin D ₃ on Days 0, 7 and 14. On Days 7, 14, and 21 subjects will return to the clinic for a post-dose blood draw and to be assessed for any signs of skin rash and/or reaction. If a subject has a skin rash and/or reaction at any time during the study, he/she should return to the clinic for assessment as soon as possible. Any rash and/or skin reaction will be photographed and diagnosed.
Eligibility Criteria (Inclusion and Exclusion):	
Inclusion criteria:
 
 Known vitamin D deficiency based on blood work obtained prior to study consent defined as serum 25-hydroxyvitamin D less than or equal to 20 ng/mL within 30 days prior to study entry. (Normal \geq to 30 µg/L total 25-OH Vitamin D) Adult, age 18 to 85 years, male or female If on oral vitamin D therapy, have been on a stable dose for the previous 90 days.

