7.2 Study Duration

The maximum duration of treatment is 14 days (study Days 0, 7 and 14). Subjects will be followed for change in vitamin D blood level and for safety until Study Day 21. It is anticipated that the study will last 4 months to enroll and complete dosing and assessment of 20 patients.

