### **1.2 Study Endpoints**

The primary endpoint is to establish the change in vitamin D blood levels following 3 doses of treatment with vitamin D gel.

Secondary study endpoints include assessment of safety, including change in parathyroid hormone level and the number of subjects who have any skin rash and/or other skin reaction following treatment with the vitamin D gel.

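### The skin-reaction count has no Day 0 score on the irritation scale and no systematic capture of reactions that clear before the 7-day visit

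*Protocol*

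**What the plan says.** Protocol 7.2 fixes the application days: "The maximum duration of treatment is 14 days (study Days 0, 7 and 14"). Protocol 13.1.1 schedules the irritation scale: an assessment of each subject's "skin will be performed on Days 7, 14 and 21 using the following scoring system for topical irritation". The lowest non-zero basic grade, 0.5, is labelled "Doubtful or negligible erythema reaction". Edema, papules, vesicles and bullae add 0.5 each.

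Day 0 skin is examined, but for another purpose. Protocol 11.1.1 lists "assessment of height, weight and skin to assess for study eligibility", and Table 1 lists skin integrity and Fitzpatrick score at that visit. Neither asks for an irritation score.

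The endpoint in SAP 1.2, repeated in Protocol 14.2, includes "the number of subjects who have any skin rash and/or other skin reaction following treatment with the vitamin D gel". It is the only secondary endpoint named in the synopsis.

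Between visits, the synopsis and Table 1 tell subjects to contact the site or come in if they notice a rash.

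**The concern.** Two gaps meet in one count.

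- **Timing.** The scale is never scheduled in the hours or days after an application. A reaction that appears and fades within the week scores 0 at the next visit. No visit procedure in Protocol 11.1.2 or 11.1.3 asks what happened since the last application.
- **Reference.** The endpoint takes any reaction, and the scale extends down to negligible erythema. Without a Day 0 score on the same scale, faint redness that was there before dosing cannot be subtracted by a stated rule.

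The first gap pushes the count down and the second can push it up. Skin findings are a named part of the safety objective, and Protocol 10.1 says that the gel base was changed from an anhydrous to a hydrous one, so readers will look to this count for local tolerability. Neither missing item can be recovered at the analysis stage.

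**Working it through.** The plan gives no expected rate, power or precision for the skin endpoint, so there is no figure of its own to reproduce. The 20 subjects in Protocol 14.4 and SAP 1.4 were chosen for the vitamin D change.

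**Step 1: timing.** Application days are 0, 7 and 14 (Protocol 7.2). Scoring days are 7, 14 and 21 (Protocol 13.1.1). The gaps are 7 − 0 = 7, 14 − 7 = 7 and 21 − 14 = 7 days. Protocol 11.1.2 allows a photograph after application, but it is optional, has no set time and carries no score.

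**Step 2: reference.** The Day 0 examination covers eligibility, skin integrity and skin type. The Day 7 and Day 14 checks are listed before that day's gel, so they precede doses 2 and 3, but they follow dose 1 or doses 1 and 2. Only Day 0 can give an untreated score for a count made per subject.

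**Step 3: the counting rule.** SAP 1.2 states no score threshold, no change from Day 0, no skin area, and no rule for reactions reported or assessed between visits.

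**Step 4: illustration of under-capture (assumed rates).** Let p be the true proportion of subjects with a short-lived reaction and d the chance that such a reaction is recorded, with n = 20 and subjects independent. Expected count = 20 × p × d. Chance of recording none = (1 − p × d)^20.

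| p | d | Expected count | Chance of recording none |
|---|---|---|---|
| 10% | 100% | 2 | 0.90^20 = 12.2% |
| 10% | 75% | 1.5 | 0.925^20 = 21.0% |
| 10% | 50% | 1 | 0.95^20 = 35.8% |
| 10% | 25% | 0.5 | 0.975^20 = 60.3% |
| 20% | 100% | 4 | 0.80^20 = 1.2% |
| 20% | 75% | 3 | 0.85^20 = 3.9% |
| 20% | 50% | 2 | 0.90^20 = 12.2% |
| 20% | 25% | 1 | 0.95^20 = 35.8% |

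If none of 20 is recorded, the upper limit of the exact two-sided 95% interval is 1 − 0.025^(1/20) = 16.8%. That limit bounds only the reactions that this schedule can detect.

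**Step 5: illustration of over-count (assumed).** Each subject is 1/20 = 5 percentage points. Two subjects with faint redness before dosing, if counted, would show as 2/20 = 10% with a true rate of zero.

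**The case against.** The strongest reply is that the plan has safeguards, and most of them are real.

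- **Subjects can report at any time.** They are told to contact the clinic, also before Day 7, and Protocol 13.2.3 requires start and stop dates for each adverse event, so a resolved reaction can be recorded. A reader might infer that short-lived reactions are simply missed; the documents do not support that. What stands is that capture depends on the subject's initiative and that scoring and counting of such reports is not specified.
- **Skin is examined on Day 0, active skin disease is excluded, and the synopsis has a physician diagnose any reaction.** A reader might infer that the plan counts pre-existing redness as a gel reaction; no passage says so, nor that a score of 0.5 alone makes a subject a reactor. What stands is that the plan leaves this open. Exclusion of skin disease does not exclude faint redness in healthy skin. The causality assessment is not tied to the endpoint, and Protocol 13.2.1 accepts as an adverse event a condition first detected after dosing even if it may have predated the study.
- **Tape.** Since "2 strips of paper tape will be applied to the" upper arms, a reader might suspect tape redness in the count. That is weak for the scheduled scores: brief redness would usually have faded by a visit 7 days later, the Day 7 and Day 14 checks come before that day's tape, and the gel line starts about 1 inch from the strips. It could matter for unscheduled or persistent findings.
- **Weight.** This is a descriptive, single-arm study of 20. With 4 of 20 the exact 95% interval is 5.7% to 43.7%, and with 2 of 20 it is 1.2% to 31.7%; they overlap heavily. Without a vehicle control, attribution to the gel is limited however Day 0 is scored. Both points are correct. They reduce the weight of the point but do not argue against collecting data that cost almost nothing.

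**Conclusion.** The point holds in a limited form. The documents establish that all scheduled irritation scores come 7 days after an application, that Day 0 has no score on that scale, and that the endpoint has no baseline comparison and no rule for reports between visits. Reactions that clear within the week are not systematically captured, and faint redness before dosing has no scored reference to remove it.

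The size is unknown. The figures above rest on assumed reaction and detection rates and show only that a modest loss of capture could change how a count from 20 subjects reads. The primary endpoint and the sample size are unaffected. It would go too far to say that this gap alone makes the count impossible to attribute to the gel, because the lack of a vehicle control limits attribution in any case. The change is worth making because it is cheap and the data cannot be obtained later.

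One editorial matter: the synopsis says both "Any rash and/or skin reaction may be photographed and diagnosed" and "Any rash and/or skin reaction will be photographed and diagnosed". These should be reconciled, but the point does not depend on them.

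**What to change.** Amend Protocol 13.1.1, Table 1 and SAP 1.2 (and Protocol 14.2 to match):

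1. At the Day 0 skin examination already scheduled, score both arms on the irritation scale before tape and gel.
2. On Days 7, 14 and 21, before any tape or gel, ask one fixed question about arm skin reactions since the last application, recording onset, duration and site. Score any unscheduled assessment on the same scale.
3. Count a subject as a reactor when a scheduled or unscheduled score in the gel area either is higher than that arm's Day 0 score and at least 1.0, or includes a supplemental sign (edema, papules, vesicles, bullae) that was absent on Day 0, whatever the total. The second condition is needed because vesicles without erythema score 0 + 0.5 = 0.5 and would be lost under a flat cut-off of 1.0.
4. Tabulate separately isolated 0.5 erythema, reactions known only from self-report, and redness confined to the tape strips.

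This is a counting rule for the endpoint only and leaves the rules on stopping treatment as they are. The cost is a few CRF fields and short wording changes, with no extra visit and no change in sample size. The drawback is that self-reported reactions are softer data, which is why they are kept apart from the main count.
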